12.3 Planned Interim Analyses

An interim analysis will be conducted after one year to examine the initial relationships between μ ORBP_{ND}, HD-tDCS, and neuropsychological results. The more complex statistical models for network analysis and HD-tDCS will be developed in subsequent years as we recruit subjects for ongoing assessment. The predictability of effects by the combination of neuropsychological and clinical tests will be used at the end of sample accrual.

12.3.1 Safety Review

Adverse events will be summarized by treatment group and categorized by severity and relationship to study procedures. If a subject has more than one occurrence of the same AE, he/she will be counted only once for that preferred term in the summary tables. The most severe occurrence of an AE and the most extreme relationship of the AE to the study procedures will be indicated in cases of multiple occurrences of the same AE.

The safety of the HD-tDCS procedure will be tested by comparing the proportion of subjects with each solicited AE in the HD-tDCS treatment group and the sham treatment group.

12.3.2 Efficacy Review

12.3.2.1 Primary Objectives

A mixed model of variance will be employed to investigate changes from baseline in clinical pain (VAS score) after 10 active daily HD-tDCS treatments including treatment group, time, and their interaction as fixed effects.

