3.2 Study Outcome Measures

3.2.1 *Primary*

The primary effectiveness endpoint will be as follows:

Change in clinical VAS pain score from baseline (Screening Day) to 4 weeks after completion of HD-tDCS sessions (Follow Up #2).

3.2.2 *Secondary*

The secondary effectiveness endpoints will include the following:

- Change in clinical VAS pain score at rest and during sustained masseteric pain stress challenge from baseline PET (#1) session to follow-up PET (#2) session, 1 week after completion of HD-tDCS sessions.
- Short- and long-term changes in GeoPain measures (pain area, intensity, and their summation) from baseline daily over the treatment period and through follow-up (1, 4, and 8 weeks after completion of HD-tDCS sessions).
- Change in μ OR BP_{ND} levels and clinical VAS pain score from baseline PET (#1) session to follow-up PET (#2) session, 1 week after completion of HD-tDCS sessions.
- Change in μ OR BP_{ND} levels at rest and during experimental sustained masseteric pain stress challenge during PET (#1) in chronic TMD patients as compared to healthy subjects.

3.2.3 *Safety*

All adverse events (AEs) will be solicited via generalized questioning at each study visit, beginning after informed consent.

In addition, questionnaires for PET Screening and HD-tDCS AEs will solicit information about the following symptoms/side effects of specific interest for HD-tDCS: headache, neck pain, scalp pain, scalp burns, tingling, skin redness, sleepiness, trouble concentrating, acute mood changes, and “other (specify).” These AEs were chosen because comprehensive reviews and a consensus article regarded them as common^{34,35}.

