5.4 Treatment Assignment Procedures

5.4.1 *Randomization Procedures*

Participants initially will be screened by phone. After clinical exam and diagnosis of the DC/TMD Axis I Group, participants will be randomized to the treatment HD-tDCS or sham groups using the Taves covariate adaptive randomization method³⁸. Using this method, a new participant will be sequentially assigned to a group based upon the previous assignments of other participants and certain covariates³⁹. The first eight TMD participants will be randomized by coin flip and the remaining TMD participants will be randomized by age and gender, following the Taves covariate adaptive randomization protocol.

5.4.2 *Masking Procedures*

The PI, Co-Investigator, and any members of the research staff who will be analyzing study data (with the exception of the coordinator[s]/biostatistician) will be masked to participant treatment. The research coordinator and any study staff who will be NOT involved in the treatment of the study participants in the HD-tDCS study component will be unmasked in order to promptly address any emergency directly or indirectly associated with the procedure for safety reasons. The research coordinators are not masked, and thus are able to blind the machines prior to administration of the stimuli. The biostatistician transmits the code to the coordinator in a manner that keeps the investigators and co-I's blinded. Patients will be allowed to know the type of stimulation they received, active or sham, at the end of the study if requested.

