Brief Pain Inventory (BPI; Short)		X			X	X	X	
Pittsburgh Sleep Quality Index		X ⁷			X	X	X	
PET Subject Information Sheet			X ⁷		X			
tDCS Effects Questionnaire				X	X	X	X	
HD-tDCS Sham/Placebo Assessment				X				
DC for TMD Symptom Questionnaire		X ⁷			X	X	X	

¹ Target dates for PET/MRI are during the week prior to Day 1 HD-tDCS session (Baseline) and during the week after completion of HD-tDCS sessions (Follow-up); an additional week window is allowed to account for scheduling issues. The "Magnetic Resonance (MR) Safety Screening Form" is completed prior to each MRI scan. See Section 2.3.4.

² Procedures may require more than one clinic visit.

³ Applicable if subject completes an in-person visit.

⁴ If subject is deemed eligible, schedule subject visits and provide subject with instructions for PET & MRI.

⁵ Missed days can be doubled in the (M-F) x 2 schedule, with study team approval. See Section 7.

⁶ These assessments will be conducted at Screening, before and after MRI/PET and tDCS Sessions, and at Follow-up visits.

⁷ Questionnaires to be completed by healthy volunteer subjects at the timepoints indicated.

⁸ HD-tDS sessions will be scheduled M-F. See Section 7.2.

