applied to the co-registered BP_{ND} scans of the same image set. The MR scans are then anatomically standardized to ICBM brain atlas stereotactic coordinates by non-linear warping, and the resulting transformation matrix applied to both K₁ ratio and BP_{ND} image sets^{47, 48, 49, 50}. As an alternative approach for Aim3, ¹H-MRS spectra will be collected from the ACC (3x2x3cm) based on our prior work showing Glx alterations in this region following tDCS therapy. Single-voxel point resolved spectroscopy (PRESS)(TR/TE=2000/35ms) will be performed using 'VAPOR' water suppression with 32 averages to measure Glx and NAA levels. A MEGAPRESS experiment, which edits out the overlapping creatine peak at 3.0ppm will measure GABA levels⁵¹. The MEGA-PRESS experiment will use: TE=68ms (TE₁=15ms/TE₂=53ms); TR=1.8s; 256 transients of 2k datapoints; spectral width=2kHz; frequency selective editing pulses (14ms) applied at 1.9ppm (ON) and 7.46ppm (OFF).

8.1.4 *Questionnaires*

To assess the primary effectiveness endpoint, clinical pain intensity at rest will be measured using the VAS at study visits shown in Table 2, Schedule of Events – II. Questionnaires. Other questionnaires listed in Table 2 will be used to address the secondary objectives of the study.

8.2 *Laboratory Procedures/Evaluations*

8.2.1 *Clinical Laboratory Evaluations*

Pregnancy and urine drug screen testing will be performed by dipstick analysis to assess eligibility criteria prior to PET scans #1 and #2.

8.2.2 *Blood Samples for Study-Specific Analyses*

If the subject consents to participate in this part of the study, serial blood samples that do not exceed a total of 45 mL (3 Tbsp) will be collected during each PET scan for analysis of inflammatory biomarkers. This blood will be collected from a separate intravenous line placed into the vein of the arm that is opposite the arm used for the tracer injection. Approximately 6 mL (0.4 Tbsp) of blood will be drawn during each PET scan at time 0, 20, 45, 65 and 80 for analysis of biomarkers. See details in MOP Section 6.6.3. The blood samples will be frozen for future testing to look at biological substances in the blood and potential hereditary traits associated with migraine.

One additional, individual collection for genetic analysis will be performed for future studies. The blood for genetic analysis will be collected prior to tracer administration and will not exceed 25 mL (2.4 Tbsp) per scan.

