12.1 Study Hypotheses

There are 6 hypotheses regarding the outcomes of this study.

12.1.1 *Hypothesis #1*

In chronic TMD subjects, ten daily sessions of active M1 modulation will result in a significant reduction in clinical pain intensity at rest compared to sham treatment, as measured by VAS scores at 4 weeks after completion of the HD-tDCS sessions.

12.1.2 *Hypothesis #2*

Ten daily sessions of M1 HD-tDCS will result in reductions in clinical (at rest) and experimental (sustained masseteric pain stress challenge) pain intensity measures in chronic TMD subjects at the time of the follow-up PET session, 1 week after completion of the HD-tDCS sessions.

12.1.3 *Hypothesis #3*

Ten daily sessions of M1 HD-tDCS will result in significant reductions in clinical pain intensity and area measures in chronic TMD subjects treated with HD-tDCS compared with those treated with a sham treatment over the short and long terms, measured by GeoPain.

12.1.4 *Hypothesis #4*

Ten daily sessions of M1 HD-tDCS will result in an increase of μ OR BP_{ND} in the thalamus and/or other pain-related regions in the brains of chronic TMD subjects from the baseline PET (#1) session to the follow-up PET (#2) session, 1 week after completion of HD-tDCS sessions.

12.1.5 *Hypothesis #5*

Ten daily sessions of M1 HD-tDCS will result in μ OR BP_{ND} changes from baseline PET (#1) session to follow-up PET (#2) session, 1 week after completion of HD-tDCS sessions that are inversely correlated with changes in mean clinical and experimental pain measures in chronic TMD subjects.

12.1.6 *Hypothesis #6*

TMD patients, compared to healthy controls, will be associated with reduction in μ OR BP_{ND} at the baseline level in the thalamus and other pain-related regions. The activation of μ OR neurotransmission, calculated as reductions in regional μ OR BP_{ND} during a sustained masseteric experimental pain challenge, will also be lower than the controls. Both these measures will be negatively correlated with clinical and experimental pain ratings. There will be no clinical trial with HD-tDCS involvement for this particular hypothesis. Hence, healthy subjects will not have stimulation and for TMD patients we will use the first, pretrial PET session (#1).

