12.2 Sample Size Considerations

For the primary objective, a sample size of 24 in each group will have 80% power to detect group differences in change in VAS pain scores with an effect size of 1.2 using a 2-group t-test with a 0.05 two-sided significance level. Our sample size of 30 subjects per group is a conservative number that takes a 20% drop-out rate into consideration.

To demonstrate correlations between changes we observe in the μ OR BP_{ND} and changes in clinical and experimental measures of pain, we will be reporting correlation coefficients for baseline levels and change scores. With 60 subjects, the confidence intervals of these correlation coefficients will be reasonably narrow for 95% confidence in these estimates. For example, an observed Pearson product-moment correlation of $p = 0.8$ would have 95% confidence interval of (0.69, 0.88).

In addition, for secondary objectives 4 and 5 we will use the PET/MRI data from up to 12 healthy controls and 12 TMD patients who were recruited and scanned during the NIDCR-NIHR56 DE022637 project.

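### The only primary model in the text (12.3.2.1) does not adjust for Screening Day VAS, age or gender, and does not name the Follow-Up #2 contrast as the primary test

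*Combined protocol and SAP*

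**What the plan says.** Section 12.3.2.1 describes a mixed model for change from baseline in VAS after "10 active daily HD-tDCS treatments including treatment group, time, and their interaction as fixed effects". It lists no covariate and no visit, and does not say which fixed effect carries the primary test.

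The target is defined elsewhere:

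- Section 3.2.1 gives the endpoint as "Change in clinical VAS pain score from baseline (Screening Day) to 4 weeks after completion of HD-tDCS sessions (Follow Up #2").
- Hypothesis #1 in 12.1.1 says active treatment "will result in a significant reduction in clinical pain intensity at rest compared to sham treatment, as measured by VAS scores at 4 weeks".
- Section 12.2 powers the trial for "group differences in change in VAS pain scores with an effect size of 1.2 using a 2-group t-test with a 0.05 two-sided significance level", with 24 evaluable per group and 80% power.

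Under 5.4.1 the first eight patients are assigned by coin flip, after which "the remaining TMD participants will be randomized by age and gender, following the Taves covariate adaptive randomization protocol".

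VAS is recorded often. Section 8.1.4 says "To assess the primary effectiveness endpoint, clinical pain intensity at rest will be measured using the VAS at study visits shown in Table 2", and footnote 6 of the Table 2 questionnaire schedule adds "These assessments will be conducted at Screening, before and after MRI/PET and tDCS Sessions, and at Follow-up visits".

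Section 12.3.2.1 sits under the interim-analysis heading. Section 12.4 leaves the final plan to a separate SAP, which section 18 lists as supplemental and which is not in the supplied text.

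**The concern.** There are two gaps.

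First, the model makes no adjustment for variables that the design already holds. Screening Day VAS enters only by subtraction in the change score, which is in general a less efficient use of baseline than a covariate. Age and gender are balanced by design but absent from the analysis. If they predict pain, an analysis that ignores them overstates the standard error.

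Second, a group, time and interaction model offers at least three candidate tests: the group difference at one visit, the group effect averaged over visits, and the overall interaction. Only the first, taken at Follow-Up #2, matches 3.2.1 and 12.1.1, and 12.3.2.1 does not select it. It does not list the levels of time either, although VAS is taken at many points.

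At stake are some precision in a 60-patient trial and an unambiguous primary result.

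**Working it through.** **Inputs from the plan:** 24 evaluable per group, effect size 1.2, two-sided 0.05, two-group t-test, 80% power (12.2). **Assumed, because the documents give neither:** correlation rho between Screening and Follow-Up #2 VAS of 0.3, 0.5 or 0.7, and k = baseline SD / follow-up SD.

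**Step 1. The plan's own figure.** By the noncentral t with 46 df, a standardised effect of 1.2 gives 98.3% power at 24 per group (12 per group would give 80.2%). The stated 80% is recovered at d = 0.826. That means 1.2 raw VAS points with SD of change 1.2/0.826 = 1.45. The plan states no SD or scale, so both readings are carried forward.

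**Step 2. Baseline VAS as a covariate, single visit.** Adjusted variance divided by change-score variance is R = (1 − rho²)/(1 + k² − 2·k·rho). With one covariate the effect is d/√(R(1 + 1/44)) on 45 df. With age and gender added and assumed uninformative, it is d/√(R(1 + 3/42)) on 43 df.

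| d = 0.826 (unadjusted 80%) | rho 0.3 | rho 0.5 | rho 0.7 |
|---|---|---|---|
| k = 1: R | 0.650 | 0.750 | 0.850 |
| baseline VAS | 93% | 89% | 85% |
| plus age, gender | 92% | 88% | 83% |
| k = 0.7: R | 0.850 | 0.949 | 1.000 |
| baseline VAS | 85% | 81% | 79% |
| plus age, gender | 83% | 79% | 77% |

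Section 5.2 excludes patients with Screening VAS below 3, which restricts the spread at baseline but not at follow-up. The equal-SD rows are therefore the favourable end.

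For d = 1.2, over k = 1, 0.8 and 0.7, power is 98.0 to 99.9% with baseline VAS and 97.5 to 99.8% with all three covariates, against 98.3% unadjusted.

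**Step 3. Interval width.** The unadjusted 95% half-width is t(46)·√(2/24) = 0.581 SD, or 0.581 × 1.45 = 0.84 VAS points. A repeated-measures model was simulated with three follow-ups, unstructured covariance, one common baseline slope, uninformative age and gender, and 1,500 trials per setting. Interval width at Follow-Up #2 relative to the unadjusted model was 0.83/0.89/0.94 at k = 1 and 0.95/1.00/1.02 at k = 0.7.

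**Step 4. Leaving out allocation factors.** If age and gender are perfectly balanced and explain a share R² of the outcome variance, the true size of the nominal 5% test is about 2·P(T46 > t(0.975)/√(1 − R²)). For assumed R² of 5, 10 and 20% this is 4.5, 3.9 and 2.9%: conservative, not inflated.

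**Step 5. Which term is tested.** Assume SD of change 1.45, correlation 0.5 between change scores, three follow-ups and 24 per group. The SD of the three-visit mean is 1.45·√((1 + 2 × 0.5)/3) = 1.19.

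- Constant 1.2-point effect: about 80% power for the Follow-Up #2 contrast and 93% for the averaged effect (d = 1.2/1.19 = 1.01). The interaction test rejects only at its 5% size, because a constant effect on change scores has no interaction.
- 2.0 points at week 3 and nothing later: the mean effect is 2.0/3 = 0.67, d = 0.56. The averaged test is significant about 48% of the time, although the true Follow-Up #2 difference is zero.

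**The case against.** The strongest reply is that the final analysis belongs to a SAP not supplied here, which may name the covariates and the contrast. That stands: the finding concerns the supplied text only, and confirmation from the SAP would close it.

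It is also fair to say that Screening VAS is not absent. It is part of the change score, and 3.2.1 fixes both the baseline and the visit for the primary endpoint. The point is lack of adjustment and an unstated link, not a missing endpoint.

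The numerical case for covariates is modest. It rests on assumed correlations and SD ratios, nearly vanishes if 1.2 is standardised, and the documents give nothing from which to size a gain from age and gender. This too stands.

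A reader might infer more from three other facts: section 18 lets the SAP change without a protocol amendment, an interim look is planned after one year, and under 5.4.2 "The biostatistician transmits the code to the coordinator". Together these could suggest that the primary model might be chosen after unblinded data are seen. The documents do not support that. Section 12.3 directs the interim look at relationships between receptor binding, HD-tDCS and neuropsychological results and does not name the primary VAS contrast, and nothing indicates a data-driven change of model. Masking and interim conduct are separate matters.

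**Conclusion.** The point holds as a specification gap that should be closed. The supplied text does not adjust the primary model for Screening Day VAS, age or gender, and does not tie it to the Follow-Up #2 contrast.

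The text does not support reading this as a biased comparison, an inflated type I error or a trial without a defined primary comparison. Omitting the covariates is unbiased on average, any effect on test size is conservative, and 3.2.1 and 12.1.1 define the comparison.

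On the raw-points reading, baseline adjustment alone ranges from a 13-point gain in power (80 to 93%) to a loss of about 1 point (80 to 79%). On the standardised reading the power change is under 2 points either way, so any useful gain is in interval width. The choice of term matters more: under the assumptions in Step 5, the averaged effect can be significant nearly half the time with no difference at the primary visit.

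**What to change.** State in 12.4 and the SAP, with a cross-reference from 12.3.2.1, or confirm that the SAP already states:

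- The primary analysis is a repeated-measures mixed model of VAS at rest at the follow-up visits, with treatment, visit, treatment-by-visit, Screening Day VAS, age and gender. Include a baseline-by-visit term if several visits are modelled.
- The single primary test is the active-minus-sham contrast at Follow-Up #2, two-sided 0.05.

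With Screening Day VAS as a covariate, this contrast is the same whether the outcome is VAS or change from Screening, so the 3.2.1 endpoint is unchanged.

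Before naming the week-3 reading, reconcile the documents on Follow-Up #1. The Schematic of Study Design and the compensation table in 5.3 list it separately from PET/MRI #2, while Table 2 merges them in Visit 4. Because VAS is taken both before and after PET/MRI, the text should say which reading counts.

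Cost: wording only, since all variables are already collected. The model spends three degrees of freedom, more with baseline-by-visit. If age and gender are uninformative they cost 1 to 2 points of power. In the least favourable assumed case (k = 0.7, rho = 0.7) full adjustment gives 77% against 80% unadjusted.

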12.3.2.2 Secondary Objectives

We will examine changes from baseline in μ OR BP_{ND} and in the activation of μ -opioid neurotransmission following 10 active daily HD-tDCS treatment. A mixed model of variance will be employed to examine change over time across the treatment groups.

Correlation will be assessed between (1) changes in μ OR BP_{ND} in the thalamus and other pain-related regions following ten M1 HD-tDCS sessions or sham treatment and (2) patient-reported changes in clinical pain (at rest) and experimental pain intensity and area measures. Correlation will be assessed using Pearson or Spearman correlation analysis, depending on the distribution of the observed data.

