3 OBJECTIVES

3.1 Study Objectives

3.1.1 *Primary Objective*

The primary effectiveness objective is to investigate whether 10 daily sessions of primary motor cortex (M1) HD-tDCS will result in a significant reduction in clinical pain intensity at rest in chronic TMD subjects 4 weeks after completion of HD-tDCS sessions, as measured by a visual analog scale (VAS) pain score.

3.1.2 *Secondary Objectives*

The secondary objectives are as follows:

- To investigate whether 10 daily sessions of M1 HD-tDCS will result in significant reductions in clinical pain intensity (at rest) and experimental (sustained masseteric pain stress challenge) measures in chronic TMD subjects at 1 week after completion of HD-tDCS sessions, as measured by VAS pain score assessments, obtained during the baseline PET (#1) session and follow-up PET (#2) session.
- To investigate whether 10 daily sessions of M1 HD-tDCS will result in significant short-term and/or long-term changes in clinical pain intensity and area measures in chronic TMD subjects treated with HD-tDCS compared to those who receive sham treatment, as measured by GeoPain measures.
- To investigate whether repetitive active M1 modulation induces increase of μ -opioid receptor (μ OR) non-displaceable binding potential (BP_{ND}) in the thalamus and other pain-related regions in the brains of chronic TMD subjects from the baseline PET (#1) session to the follow-up PET (#2) session, 1 week after completion of HD-tDCS sessions.
- To investigate whether any μ OR BP_{ND} changes from baseline PET (#1) session to follow-up PET (#2) session are associated with changes in mean clinical and experimental pain measures, as measured by VAS pain scores in chronic TMD subjects who receive HD-tDCS treatment compared to those subjects who receive sham treatment.
- To investigate whether chronic TMD is associated with μ OR BP_{ND} changes as compared to healthy subjects during baseline PET (#1) session at rest, and during experimental sustained masseteric pain stress challenge.

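### The correlation of BPND change with pain change has no stated arm term; if it is pooled, and active treatment shifts both measures as predicted, arm means alone push it negative

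*Combined protocol and SAP*

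**What the plan says.** Section 12.3.2.2 has two parts. For BPND itself, arms are compared: "A mixed model of variance will be employed to examine change over time across the treatment groups". For the association, it correlates changes in BPND "in the thalamus and other pain-related regions following ten M1 HD-tDCS sessions or sham treatment" with changes in clinical and experimental pain, by Pearson or Spearman depending on the distribution. The second part does not say whether this is one correlation over both arms, one per arm, or one adjusted for arm.

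Other sections point in different directions:

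- Section 12.2 says "we will be reporting correlation coefficients for baseline levels and change scores", and then "With 60 subjects, the confidence intervals of these correlation coefficients will be reasonably narrow for 95% confidence in these estimates". Its example is r = 0.8 with interval (0.69, 0.88).
- The fourth secondary objective in 3.1.2 frames the association "in chronic TMD subjects who receive HD-tDCS treatment compared to those subjects who receive sham treatment".
- Hypothesis #5 in 12.1 refers to BPND changes after active sessions "that are inversely correlated with changes in mean clinical and experimental pain measures in chronic TMD subjects".
- Section 12.2 adds that "for secondary objectives 4 and 5 we will use the PET/MRI data from up to 12 healthy controls and 12 TMD patients" from an earlier project. The fourth objective as listed is this association. The text does not say whether those scans enter the change-score correlation.

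Section 12.3.2.2 sits under the planned interim analyses, and 12.4 leaves the final plan to a separate SAP whose text is not in the document.

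**The concern.** Hypothesis #5 carries the mechanistic claim that μ-opioid change goes with pain relief. Hypotheses #4 and #2 predict that active treatment raises BPND and lowers pain. If both happen relative to sham, the active subjects sit together at high BPND change and low pain change, and the sham subjects sit at the opposite corner. A single correlation drawn through both groups is then negative even if, within each arm, a subject's BPND change says nothing about that subject's pain change. A reported inverse correlation could partly restate two treatment effects and be read as evidence of mechanism. From the protocol text alone, a reader could not tell which of the three analyses had been fixed in advance.

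**Working it through.** **The plan's own figure.** The Fisher interval is tanh(atanh(r) ± 1.96/√(n-3)). With r = 0.8 and n = 60, atanh(0.8) = 1.0986 and 1.96/√57 = 0.2596. The interval is (0.685, 0.876), which rounds to the stated (0.69, 0.88). The example therefore uses both arms together. That does not prove pooling of the change scores, because the same sentence covers baseline correlations. Those are pre-randomisation and need no arm term; Hypothesis #6 also plans some ("Both these measures will be negatively correlated with clinical and experimental pain ratings").

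**Inputs for the artefact.**
- Allocation is 1:1, with 30 per arm, or 24 after the 20% dropout in 12.2 (30 × 0.8).
- Within-arm correlation is set to ρ = 0 and within-arm SDs to 1.
- d1 is the fall in pain and d2 the rise in BPND, active against sham, in SD units. The documents give no BPND effect size, so d2 is an assumption.
- 0.83 SD is the shift that a two-group t-test detects with 80% power at 24 per arm (0.826). The 1.2 in 12.2, read as SD units, would give 98% power there, so it serves only as an upper bound. Both values derive from the 4-week VAS endpoint. Applying them to 1-week changes and to BPND is a further assumption.

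**Formula.** Pooled r = (ρ - d1·d2/4) / √[(1 + d1²/4)(1 + d2²/4)].

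With ρ = 0:
- 0.5 and 0.5: -0.0625/1.0625 = -0.059
- 0.83 and 0.83: -0.1722/1.1722 = -0.147
- 1.2 and 1.2: -0.36/1.36 = -0.265
- either shift zero: 0

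**How often it would matter.** The plan states no test of the correlation, so exclusion of 0 by the 95% interval is used as a gauge (40,000 simulated trials per case, Pearson, ρ = 0). Ranges run over 24 and 30 per arm.

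| Shift in both (SD) | Pooled r | r below 0 | Interval excludes 0 |
|---|---|---|---|
| 0.5 | -0.06 | 66-68% | 7.0-7.4% |
| 0.83 | -0.15 | 86-88% | 17-21% |
| 1.2 (upper bound) | -0.26 | 98% | 46-56% |

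If only one measure shifts, exclusion is 5.0-5.2%. Adjusted for arm, it is 4.9-5.3% in every case.

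**A real association is also distorted.** With ρ = -0.30, pooled r is (-0.30 - 0.0625)/1.0625 = -0.34 at 0.5 SD and (-0.30 - 0.1722)/1.1722 = -0.40 at 0.83 SD. If BPND fell instead, the shift term changes sign and the results are -0.22 and -0.11.

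**Cost of adjusting.** One more degree of freedom replaces n-3 by n-4. At n = 60 and r = 0.8 the interval becomes (0.684, 0.877). With no treatment effect and ρ = -0.30, power is 55-65% adjusted against 56-66% pooled.

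**By-arm precision.** At r = 0.8 the interval is (0.62, 0.90) with n = 30 and (0.59, 0.91) with n = 24. For the difference between arms, SE(z) = √(2/27) = 0.272 at 30 per arm and √(2/21) = 0.309 at 24. Power for 0.5 against 0 is about 52% and 43%.

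**The case against.** Pooling is an inference. The objective's comparison with sham and Hypothesis #5's restriction to active sessions both lean by-arm, the n = 60 statement also covers baseline correlations, and the unseen SAP may settle the matter. All of this stands, so the point is about an open choice with a known hazard, not a demonstrated error.

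Three stronger readings are tempting, and the documents do not support them.
- A reader might infer that pooling by itself biases the result towards Hypothesis #5. It does not: both measures must shift between arms, in the predicted directions. Section 2.1.3 reports decreased thalamic receptor availability during active tDCS. That is an acute finding at a different time point, but it shows that the direction of any BPND shift is a hypothesis.
- A reader might infer that nothing in the plan answers the active-versus-sham wording of the objective. If 12.3.2.2 means one correlation per arm, it supplies the two estimates to compare. It is only unclear whether any stated analysis does so.
- A reader might take the 46-56% figure as the expected error rate. It needs 1.2 SD on both measures, and nothing supports that for BPND.

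For experimental pain the artefact is probably smaller, because the closed-loop infusion in 8.1.2 holds intensity to a common target of 40 out of 100.

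It can also be said that an arm-adjusted correlation is itself a choice of estimand, named by neither Hypothesis #5 nor the objective. That is fair, and it is why the within-arm estimates and their difference belong beside it.

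**Conclusion.** The concern holds in conditional form. Section 12.3.2.2 followed as written most readily gives a pooled, unadjusted correlation. If that is what is done, and if active treatment both raises BPND and lowers clinical pain relative to sham, the result is biased towards the predicted sign. The bias is small at modest shifts and material only when both measures move substantially. Its size rests on assumed shifts, zero within-arm correlation, normal data and Pearson's coefficient; the mechanism is the same for ranks, but those figures were not computed. This is a secondary objective, and the primary analysis is untouched. The change should still be made, preferably before the one-year interim look at these relationships, because adjustment removes the artefact at almost no cost in precision.

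**What to change.** In 12.3.2.2 and the SAP, state that the change-score association is adjusted for arm: partial Pearson, or partial Spearman on ranks if the data are non-normal. Report the active and sham within-arm correlations with 95% intervals. Give their difference as a low-precision estimate that answers the comparison in 3.1.2.

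In 12.2, separate baseline from change-score correlations and quote the 24- and 30-per-arm intervals shown above beside the n = 60 figure. State that the change-score correlation uses only subjects randomised in this trial. Scans from the earlier project can still serve the baseline comparisons and the baseline correlations of Hypothesis #6.

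The cost is a few sentences, one degree of freedom (a change in the third decimal of the n = 60 interval), and by-arm precision that looks less favourable than the present figure. No new data are needed.
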